3.5. Escape Medication

For participants with measured myopia progression ≥ 2.00 D from baseline in SE at a visit occurring between Month 18 and Month 36 (inclusive), and measurements obtained 6 months later at the next scheduled visit to confirm myopia progression (ie, confirmation at a visit between Month 24 and Month 42 [inclusive]), then treatment with escape medication (active SYD-101 0.03%) will be initiated at the confirmatory visit and continued until Month 48.

Participants on escape medication will adhere to the same visit schedule. No medications will be dispensed during or after the Month 48/End of Study (EOS) visit. As with masked study treatment, open-label SYD-101 0.03% (escape medication) will be provided by the sponsor, managed and tracked using IVRS/IWRS, and dispensed to participants by the assigned site staff.

4. General Statistical Considerations

All statistical analyses will be conducted using SAS Version 9.4 or higher (SAS Institute, Cary, North Carolina).

All statistical tests will be two-sided and will be performed at the 5% level of significance leading to 95% (2-sided) confidence intervals (CIs), unless otherwise stated. P-values will be rounded to 3 decimal places. If a p-value is less than 0.001 it will be reported as “<0.001.” If a p-value is greater than 0.999 it will be reported as “>0.999.”

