4.1. Sample Size

Group sample sizes of 280 in each treatment arm will achieve at least 90% power to detect a difference in the percentage of participants with myopic progression (>0.75 D) of at least 15% between a SYD-101 arm and Vehicle. Power calculations presented in Figure 4-1 are based on the Chi-squared test at a 2-sided significance level of 0.025.

[figure not shown]
Figure 4-1 Power for 2-Sided Chi-Square Test Evaluated at Alpha=0.025 for Proportion Responders When 280 Participants Per Arm

Additionally, group sample sizes of 280 per treatment arm achieves >90% power to detect a reduction of 0.18 D or more in the annual progression rate between SYD-101 and Vehicle, assuming a common SD of 0.60 D. Power calculations presented in

Figure 4-2 are based on a 2-sample t-test evaluated at the 0.025 significance level.

Figure 4-2 Power for 2-Sided T-Test Evaluated at Alpha=0.025 for Annual Progression Rate When 280 Participants Per Arm

Furthermore, to estimate the statistical power of the two region- specific primary endpoints, simulations based on various assumptions regarding the mean vehicle annual progression rate, the mean active annual progression rate based on % reduction from the vehicle annual progression rate, the SD for the APR as well as allowing for participant dropout/study treatment discontinuation and escape medication have been considered to investigate statistical power for a range of sample sizes. Simulations were run after the protocol was finalized to assess protocol sample size assumptions. For the most likely assumption of parameters examined, a mean placebo/control APR of 0.65 D and a mean active APR 0.325 D (a 50% reduction from the mean vehicle/control APR) both with a SD of 0.55 D and an annual dropout/study treatment discontinuation rate of 7%, a sample size of 217 participants per treatment arm provides an approximate 97% power for the FDA endpoint and an approximate 99.96% power for the EMA endpoint assuming a significant level of 0.025.

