To evaluate the potential rebound effect once participants discontinue SYD-101 therapy, exploratory analyses will be conducted on the set of participants initially randomized to SYD-101 (0.01% or 0.03%) at Baseline and who are re-randomized to Vehicle at Month 36. The mean annual progression rate from baseline to Month 36 will be numerically compared to the mean annual progression rate from Month 36 to Month 48 within this set of participants. For comparison, the same summaries will be presented for participants randomized SYD-101 therapy and who are not re-randomized to Vehicle at Month 36. Summary statistics will be presented by initial randomization group.

To evaluate the potential rebound and re-treatment effect once participants discontinue SYD-101 therapy, exploratory analyses will be conducted on the set of participants initially randomized to SYD-101 (0.01% or 0.03%) at Baseline and who are re-randomized to Vehicle at Month 36. The mean annual progression rate from Baseline to Month 36 will be numerically compared to the mean annual progression rate from Month 36 to Month 48 within this set of participants to investigate rebound. For comparison, the time intervals will be summarized for participants randomized SYD-101 therapy and who are not re-randomized to Vehicle at Month 36. Additionally, these summaries will also be subset by receipt of escape medication after Month 36.

To evaluate the escape medication effect, select summaries and plots will be provided by numerically comparing the participants who never received escape medication and the participants who received escape medication at Month 24, Month 30 and Month 36 by initial randomization group. Summaries and plots will be presented from Baseline to Month 36, and will include:

- Mean change from baseline in SE
- Mean annual progression rate

- Mean change from baseline in axial length

Select summaries will be provided for the subset of participants initially randomized to SYD-101 (0.01% or 0.03%) at Day 1 (Baseline) and re-randomized to SYD-101 at Month 36 and who remain on SYD-101 for the entire duration of the study. This will be done to characterize the efficacy profile of those participants receiving up to 48 months of SYD-101 treatment. Summaries to be presented for this subset of participants includes:

- Mean change from baseline in SE
- Mean annual progression rate from baseline to Month 48
- Proportion of participants with myopic progression >0.75 D at or before Month 48

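### SAP 8.3 judges the escape-medication effect on change from study baseline to Month 36 against never-escaped children, a level contrast driven by who qualifies for escape; Month 36 starters have no escape exposure in that window.

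*SAP*

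**What the plan says.** SAP 8.3 (Other Efficacy Endpoints) states the aim and the form of output: "To evaluate the escape medication effect, select summaries and plots will be provided". The comparison is made by "numerically comparing the participants who never received escape medication and the participants who received escape medication at Month 24, Month 30 and Month 36", split by initial randomization group. On the window it says "Summaries and plots will be presented from Baseline to Month 36". The three listed measures are "Mean change from baseline in SE", the mean annual progression rate, and mean change from baseline in axial length.

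Four other places determine what this comparison contains.

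- **Who escapes.** SAP 3.5 requires "measured myopia progression ≥ 2.00 D from baseline in SE at a visit occurring between Month 18 and Month 36", confirmed at the next scheduled visit six months later. SAP 4.2 makes clear that the confirming measurement must also show at least 2.00 D from baseline.
- **When escape starts.** SAP 3.5 and 7.3.1 place it at the confirmatory visit, so the earliest per-criteria start is Month 24.
- **How the rate is computed.** SAP 8.1.1 takes the whole change in SE from study baseline, divides by the days since first dose and multiplies by 365.25.
- **What is planned after Month 36.** Protocol 9.4.9 allows the Month 36 to 48 groupings to be refined by escape at Months 24 to 42. SAP 8.3 allows it only for escape after Month 36. Under SAP 3.1 and 4.2, children already on escape by Month 36 stay on it, so they belong to none of the five re-randomization pathways listed in SAP 8.3.

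**The concern.** The question is about what happens after a child starts escape, but every listed measure runs from study baseline. For a Month 24 starter two thirds of the window precedes escape, for a Month 30 starter five sixths, and for a Month 36 starter all of it.

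The groups are also sorted on the outcome. A per-criteria escaper has at least 2.00 D of progression by the start of escape, and that amount enters the change in SE and the annual rate. The never-escaped group consists mainly of children who did not reach that amount. Axial length is affected through the same selection, though no threshold applies to it directly.

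In the SYD-101 0.03% arm, escape is the strength already assigned (SAP Table 7-1), so there is no change of strength to evaluate.

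At stake is a table labelled as the escape effect in which escapers look much worse than non-escapers even if the drug works. Visits that could describe the effect fall partly outside the window.

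**Working it through.** The documents give no planned size or estimate for this comparison, so there is no stated figure to reproduce.

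**Inputs.** Target days are Month 18 = 546, Month 24 = 728, Month 30 = 910, Month 36 = 1092 and Month 48 = 1456 (SAP Table 4-1). The threshold is 2.00 D at two consecutive six-monthly visits (SAP 3.5, 4.2). The rate formula is in SAP 8.1.1. SAP 4.1 gives the planning values: "a mean placebo/control APR of 0.65 D and a mean active APR 0.325 D", with SD 0.55.

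**Step 1: escape exposure inside the window** = 1092 − start day.

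| Escape start | Days on escape by Month 36 | Share of window | Days from start to Month 48 |
|---|---|---|---|
| Month 24 | 1092 − 728 = 364 | 33.3% | 728 |
| Month 30 | 1092 − 910 = 182 | 16.7% | 546 |
| Month 36 | 0 | 0% | 364 |

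**Step 2: rate under complete arrest.** A child at exactly 2.00 D when escape starts, with no further progression, has a Month 36 rate of 2.00 / 1092 × 365.25 = 0.669 D/year. The planning Vehicle mean is 0.65 D/year.

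**Step 3: size of the contrast, as an illustration.** Assumptions that are not in the documents: each child progresses linearly, individual rates are Normal with the planning mean and SD, every qualifier takes escape, and there is no measurement error. A child then starts escape at Month 24 if the rate is at least 2.00/546 × 365.25 = 1.34 D/year. The start is Month 30 for rates from 2.00/728 × 365.25 = 1.00 up to 1.34, and Month 36 for rates from 2.00/910 × 365.25 = 0.80 up to 1.00. Group means are means of the truncated Normal. If escape cuts the rate by a fraction e, the Month 36 rate is the pre-escape rate × [start day + (1 − e) × (1092 − start day)] / 1092.

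Vehicle arm, mean 0.65, SD 0.55, Month 36 rate in D/year:

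| Group | e = 0 | e = 50% | e = 100% |
|---|---|---|---|
| Month 24 starters | 1.60 | 1.33 | 1.07 |
| Month 30 starters | 1.15 | 1.06 | 0.96 |
| Month 36 starters | 0.90 | 0.90 | 0.90 |
| Never escaped | 0.30 | 0.30 | 0.30 |

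Under these assumptions about 39% of Vehicle children escape by Month 36 (share with a rate of at least 0.80). That high share is what pulls the comparator down to 0.30.

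**Step 4: sensitivity, complete arrest.**

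| Mean, SD (D/year) | Measurement SD | Month 24 / 30 / 36 starters | Never escaped |
|---|---|---|---|
| 0.65, 0.55 | 0.25 D | 1.03 / 0.96 / 0.92 | 0.31 |
| 0.65, 0.35 | 0.125 D | 0.95 / 0.93 / 0.89 | 0.46 |
| 0.325, 0.55 | none | 1.04 / 0.95 / 0.90 | 0.14 |

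The direction is the same throughout; the size depends on the assumed spread of rates.

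**Step 5: anchoring at escape start.** With a true 50% effect in the Step 3 setting, the before and after rates are 1.60 and 0.80 for Month 24 starters and 1.15 and 0.58 for Month 30 starters. With measurement SD 0.25 D they are 1.55 and 0.77, and 1.15 and 0.55. The effect is recovered. A drug with no effect can still show a small apparent drop: with mean 0.325 and measurement SD 0.25 D, Month 30 starters go from 1.13 to 1.09. Natural slowing with age, which this model omits, would add to it.

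**The case against.** Four points on the other side have force.

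- **By-visit output carries information.** A reader might infer that the result is fixed by the entry rule whatever the drug does. The documents do not support that. SAP 8.3 promises plots as well as summaries, and SAP section 8 says efficacy endpoints are summarized by visit. Curves grouped by escape-start visit could show a bend after Month 24 or Month 30, and the Month 24 starters' rate in Step 3 moves from 1.60 to 1.07 with the drug effect. Only the Month 36 group is unaffected by the drug.
- **Later data are not ignored outright.** A reader might also infer that SE at Months 42 and 48 goes unused for escapers. Protocol 9.4.9 permits refining the Month 36 to 48 summaries by escape at Months 24 to 42, and for Month 36 starters the Month 36 anchor is the escape start. It also plans a switch-anchored rate for SYD-101 children re-randomized to Vehicle who then escape. SAP section 4 splits tables by initial and current treatment. But the refinement is optional, SAP 8.3 narrows it to escape after Month 36, and no before/after rate is specified for Month 24 to 36 starters.
- **The 2.00 D floor is not strict.** SAP Table 3-2 contemplates sites treating before the criteria are met, and such a child could have progressed less.
- **The stakes are limited.** The comparison is numerical, exploratory and carries no alpha. The primary and secondary estimands handle escape by their own rules.

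The arms are also already shown separately; what the 0.03% arm lacks is a label saying that escape there continues the same strength. These points narrow the problem. They do not rescue the level contrast with never-escaped children.

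**Conclusion.** The concern holds in limited form. As specified, the contrast between escapers and never-escaped children on baseline-anchored measures to Month 36 cannot be read as an escape effect. This follows from the definitions: the qualifying progression lies inside the SE outcome for per-criteria escapers, and exposure in the window is 33%, 17% and 0%. Complete arrest at the threshold still gives 0.67 D/year. In the illustrative Vehicle arm, a fully effective drug would leave escapers at 0.90 to 1.07 D/year against 0.30 in never-escaped children; with a narrower spread of rates the gap is 0.89 to 0.95 against 0.46. Those figures rest on linear progression, Normal rates and full uptake, and show direction and rough size only.

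The documents do not support extending this to the trial's efficacy conclusions. It concerns one exploratory summary that should be corrected because its label promises an answer its construction does not give.

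**What to change.** Amend SAP 8.3 as follows.

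- For children who start escape at Months 24 to 36, report the annual SE rate from the escape-start visit to Month 48 beside the same child's rate from baseline to escape start, by initial arm and escape-start visit. State that regression to the mean limits the before/after figures.
- Report axial length this way only for Month 24 and Month 36 starters. Biometry is annual, so Month 30 starters have no measurement at escape start.
- Label the SYD-101 0.03% arm as continuation of the same strength.
- If the baseline-to-Month 36 display is kept, describe it as descriptive and do not present its contrast with never-escaped children as evidence of an escape effect.
- A concurrent reference of same-arm children with similar progression who did not start escape is optional. It is usable only where such children exist and only before Month 36, when assigned treatment changes. It gives nothing for Month 36 starters and one six-month interval for Month 30 starters.
- Reconcile the protocol, under which escape may be started, with SAP 3.5, under which it will be. This determines whether qualified but untreated children sit in the never-escaped group. Reconcile also the differing escape refinements in Protocol 9.4.9 and SAP 8.3.

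The cost is SAP wording and a few extra tables from data already scheduled for collection, with no added visits. The downside is that the replacement is an uncontrolled before/after comparison.

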8.4. Quality of Life (QOL) Questionnaire

The investigator’s designee will administer a questionnaire to participants (or parents/guardians) to assess potential impact of treatment on the participant’s QOL. Responses will be marked as strongly agree, agree, neither agree or disagree, disagree, strongly disagree. There are eight questions in all. Questions 2 to 7 will be scored from 5 for strongly agree to 1 for strongly disagree and questions 1 and 8 will be reversed scored from 1 for strongly agree to 5 for strongly disagree so that higher values consistently indicate a “worse” outcome for the participant.

Summary statistics will be presented for each question as well as for the per participant average of the 8 questions. Participants will be included in the analysis of average question score if they have at least 4 non-missing question responses. For the average question score, missing question responses will be imputed from the mean of the available question responses.

Additionally, a Wilcoxon Rank Sum test and frequency tables will be presented summarizing

results and individual participants responses will be listed. The Wilcoxon Rank Sum test will be performed in a pairwise manner comparing each treatment dose (SYD-101 0.01%, SYD-101 0.03%) to vehicle. The ranks are based on the observations of the two groups that are compared, p-values from the exact Wilcoxon Rank Sum test as well as the Hodges-Lehman estimates ([Hodges, J. L.; Lehmann, E. L. \(1963\)](#)), and Moses 95% CI ([Moses, Lincoln E. \(1965\)](#)) will also be presented for supportive use. No adjustment for type 1 error will be made for the multiple dose comparisons or multiple timepoints.

9. Safety Analysis

Safety will be assessed through summaries of AEs and changes in vital signs, BCVA, biomicroscopy, IOP, and ophthalmoscopy abnormalities. Safety data will be summarized by treatment group using the Safety Set.

In general, for ocular assessments, safety will be summarized using the average of both eyes averages, with a few exceptions where presenting data for the eye with the worse response for the given assessment. Percentages, if applicable, will be calculated based on the number of participants in the Safety Set. For analysis of event data, participants will be counted once for given event if the event occurs in at least one eye.

For safety analyses from baseline to Month 24, the baseline will be considered the start of study prior to dose of any study medication. Unless otherwise specified, for safety analyses at Month 36, at Month 48, or from Month 36 to Month 48, data will be summarized based on treatment being taken at the time of event occurrence/assessment, including those who take SYD 101 0.03% as escape medication or who are re-randomized to Vehicle at Month 36. Participants who receive escape medication or who are re-randomized at Month 36 will be included under each treatment received during the analysis period. Percentages, if applicable, will be calculated based on the number of participants in the Safety Set who received at least one dose of the given treatment. For each treatment received, the baseline value will be the last non-missing assessment prior to initiation of the given treatment. (For participants originally randomized to SYD 101 0.03%, who are rerandomized to Vehicle at Month 36, and then subsequently switch to open label SYD 101 0.03% as escape medication, assessments made on SYD 101 0.03% will use the last non-missing value on or prior to Day 1/date of first SYD 101 0.03% treatment as baseline.) Total summaries will include data from assessments during the first 24 months while participants should be on their original randomized treatment only.

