3.1. Overall Study Design and Plan

This is a 48-month, Phase 3, multicentered, randomized, double-masked, vehicle-controlled study to assess the safety and efficacy of SYD-101 eyedrops in male and female children between 3 and 14 years of age (inclusive) with myopia of 0.50 D to 6.00 D (inclusive). Clinical sites in the US and in Europe will participate in this study. A total enrollment of approximately 840 pediatric participants is planned for this study. The study will have 3 treatment groups: SYD-101 0.01%, SYD-101 0.03%, and the Vehicle of SYD-101.

Participants will be assessed according to the schedule of procedures and assessments.

Allocation to study treatment will occur in a double-masked manner on 2 occasions:

- initial randomization at Baseline (for Primary Treatment Period [Part 1]) will be in a 1:1:1 ratio of SYD-101 0.01%: SYD-101 0.03%: Vehicle and stratified by baseline spherical equivalent (SE, 0.50 D to 3.0 D and >3.0 D to 6.0 D) and age (3 years to <6 years, 6 years to <9 years, 9 years to <12 years, and 12 years to 14 years)
- re-randomization at Month 36 (for Randomized Withdrawal Period [Part 2]): participants who were initially assigned (at Baseline) to SYD-101 0.01% will be re-randomized in a 1:1 ratio to masked SYD-101 0.01% or Vehicle; participants initially assigned (at Baseline) to SYD-101 0.03% will be re-randomized in a 1:1 ratio to masked SYD-101

0.03% or Vehicle; all participants initially assigned (at Baseline) to Vehicle will be re-assigned to receive masked SYD-101 0.03%. Re-randomization of SYD-101 participants will not be stratified. Participants who have escaped to open-label SYD-101 0.03% therapy at or prior to Month 36 will remain on escape medication

There are 3 planned database locks for this study. The first will occur after all participants have completed the Month 24 visit and any required confirmatory visits for the purpose of submitting data for EU regulatory submission to the EMA (ie, Month 24 analysis). The second database lock will occur after all participants have completed the Month 36 visit and any required confirmatory visits for US regulatory submission to the FDA (ie, Month 36 analysis). The final database lock will occur after all participants have completed the last study visit (Month 48 or ET) to allow assessment of the persistence of effect of SYD-101 after 12 months of randomized withdrawal (ie, Month 48/Final analysis).

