Time to progression of myopia will be calculated in days as the date of first confirmed SE measurement that represents a reduction of >0.75 D or greater minus the date of first dose of study drug, plus one. Participants who do not experience myopic progression through 24 months (EMA) or 36 months (FDA) or who have an early discontinuation without a progression will be censored at the date of their last SE assessment at or before Month 24 (EMA) or Month 36 (FDA). Participants who receive a prohibited treatment or escape therapy prior to myopic progression will be censored as of the date they received the prohibited or escape therapy. Observations after treatment discontinuation will be included as observed. Each dose of SYD-101 will be compared to Vehicle for time to progression of myopia using the log-rank test stratified by the randomization stratification factors. Kaplan-Meier estimates of the distribution of time-to-event will be tabulated and plotted by treatment group. The tabulation will include the Kaplan-Meier estimate of the medians, 25th and 75th quartiles, and 95% CIs (if estimable). The number and percent of participants censored and with events will be presented.

For all secondary endpoints excepting axial length, time to progression, and the Fast Progression subgroups, intercurrent events will be handled as specified in [Table 3-5](#). Data will be multiple imputed assuming MAR for intermittent missing data. Observations after prohibited or escape treatments will be multiply imputed assuming MAR. Observations after discontinuation of treatment or study due to a related AE will be multiply imputed assuming MNAR using a sequential vehicle-based pattern regression. Observations after discontinuation of treatment or study not due to a related AE will be multiply imputed assuming MAR.

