8.3. Other Efficacy Endpoints

Data collected after Month 36 will be considered exploratory analysis and summarized separately using descriptive statistics only and based on observed data. Participants will be grouped by treatment pathway from the start of study through the re-randomization (original SYD-101 0.01% and SYD-101 0.03% participants) and transition to active treatment (original Vehicle participants) at Month 36:

- Participants initially randomized to SYD-101 0.01% at Baseline and re-randomized to SYD-101 0.01% at Month 36
- Participants initially randomized to SYD-101 0.01% at Baseline and re-randomized to Vehicle at Month 36
- Participants initially randomized to SYD-101 0.03% at Baseline and re-randomized to SYD-101 0.03% at Month 36
- Participants initially randomized to SYD-101 0.03% at Baseline and re-randomized to Vehicle at Month 36

- Participants initially randomized to Vehicle at Baseline and re-assigned to SYD-101 0.03% at Month 36

In general, data collected after Month 36 will be summarized according to the above groupings. As applicable, the groupings above may be further refined based on receipt of escape medication after Month 36. Changes in continuous measures will be relative to the data collection at the Month 36 visit, unless otherwise specified.

Summaries to be provided for the grouping above include:

- Mean change from Month 36 in SE
- Mean annual progression rate from Month 36 to Month 48
- Proportion of participants with myopic progression from Month 36 >0.75 D
- Proportion of participants with annual myopia progression rate from baseline to Month 48 ≤ 0.50 D/year
- Proportion of participants with annual myopia progression rate from baseline to Month 48 ≤ 0.25 D/year
- Proportion of participants with increase from baseline of myopia of >0.50 D at Month 48
- Mean change in axial length from Month 36 to Month 48

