9.4. Pregnancy Test

Serum pregnancy testing will be performed on an annual basis using human chorionic gonadotropin pregnancy urine dipstick test (female participants of childbearing potential only.) Pregnancy testing results will be listed.

10. Interim Analysis

There are no interim analyses planned for this study. Analyses performed at Month 24 for the EMA Submission are considered the final analysis of primary efficacy for that submission. Analyses performed at Month 36 for the FDA Submission are considered the final analysis of primary efficacy for that submission.

11. Changes in Planned Analysis

With protocol amendment 3, intercurrent event analysis has been expanded to include 6 sensitivity analyses per FDA and EMA primary and key secondary efficacy endpoint and the intercurrent event approaches for all endpoints have been modified from original protocol incorporating regulatory feedback from the FDA and EMA. An additional subgroup for fast-progressors has been added to the EMA endpoint to be included in secondary analysis. Statistical testing will be performed for QOL assessments for informational purposes.

12. Impact of COVID-19 on the Planned Analyses

On January 31, 2020, the Department of Health and Human Services issued a declaration of a public health emergency related to the Coronavirus Disease 2019 (COVID-19) acute respiratory disease, and on March 13, 2020, the President declared a national state of emergency. The Food and Drug Administration has recognized that the COVID-19 pandemic may impact the conduct, evolution, and statistical analyses of clinical trials across therapeutic areas (March and June 2020). Participants with missing clinic visits due to COVID-19 will be listed; participants were able to complete questionnaires via phone.

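### The QOL dose-versus-Vehicle rank tests in SAP 8.4 ignore the randomization strata, so they are valid but conservative to the extent that age or baseline SE predicts QOL

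*SAP*

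**What the plan says.** SAP 8.4 describes an eight-item questionnaire answered by participants or their parents or guardians. It plans summary statistics for each question and for the average score, frequency tables, and a rank test: "The Wilcoxon Rank Sum test will be performed in a pairwise manner comparing each treatment dose (SYD-101 0.01%, SYD-101 0.03%) to vehicle". The ranking is over the two arms pooled: "The ranks are based on the observations of the two groups that are compared". The p-value comes from the exact test, with a Hodges-Lehmann estimate and a Moses 95% interval as support. No stratification factor, analysis set or list of visits is given. On multiplicity it says: "No adjustment for type 1 error will be made for the multiple dose comparisons or multiple timepoints". SAP Section 11 gives the tests their status: "Statistical testing will be performed for QOL assessments for informational purposes".

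SAP 3.1 states that initial randomization is "stratified by baseline spherical equivalent (SE, 0.50 D to 3.0 D and >3.0 D to 6.0 D) and age", with age in four classes between 3 and 14 years. That makes 2 x 4 = 8 strata.

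The other between-arm efficacy analyses treat baseline factors as follows:
- Proportion endpoints (SAP 8.1.1 and 8.2): CMH tests that account for the baseline SE and age categories.
- Time to progression (SAP 8.2): compared "using the log-rank test stratified by the randomization stratification factors".
- Annual progression rate (SAP 8.1.1): MMRM with age category and baseline SE.
- Axial length (SAP 8.2): MMRM with age category and baseline axial length.

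**The concern.** When allocation is balanced within strata, differences between strata cannot contribute to the difference between arms. A test that ranks all children together still counts that between-stratum spread as noise, so its reference distribution is wider than the one the design produces. The p-values are then too large on average.

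This matters only if the strata predict the score. That is plausible here, because the children are aged 3 to 14 and either the child or a parent may answer, but the documents give no data on it. What is at stake is sensitivity: QOL is collected to detect an impact of nightly drops on the child, and a conservative test makes a modest impact harder to see. The SAP gives no reason for leaving the strata out of this one between-arm test.

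**Working it through.** The documents state no sample size, power or size figure for the QOL tests, so there is no plan figure to reproduce.

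**Inputs from the documents.** Planned n = 280 per arm (SAP 4.1); 8 strata (SAP 3.1); nominal two-sided 5% level (SAP Section 4).

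**Assumed inputs.** Share of score variance explained by the strata, R² = 0, 5%, 10% or 20%; a treatment shift of 0.24 residual SD; roughly normal scores within strata. None of these stands in the documents.

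**Size of the unstratified test.** Under stratified allocation the test statistic has true variance of about (1 − R²) times the variance that the test assumes. The true size is therefore 2 × [1 − Φ(1.96/√(1 − R²))].
- R² = 5%: 1.96/√0.95 = 2.011, size 4.4%.
- R² = 10%: 1.96/√0.90 = 2.066, size 3.9%.
- R² = 20%: 1.96/√0.80 = 2.191, size 2.8%.
- R² = 0: 1.96, size 5.0%.

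**Power.** For a stratified rank test the standardized shift is about 0.24 × √(280/2) × √(3/π) = 0.24 × 11.83 × 0.977 = 2.775. Power is Φ(2.775 − 1.96) = 79.2%. The unstratified test must pass the larger thresholds above:
- R² = 5%: Φ(2.775 − 2.011) = 77.8%, a loss of 1.5 points.
- R² = 10%: Φ(2.775 − 2.066) = 76.1%, a loss of 3.2 points.
- R² = 20%: Φ(2.775 − 2.191) = 72.0%, a loss of 7.2 points.

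**Simulation 1.** 4,000 runs per case, 280 per arm, assumed age shares 5/25/40/30% and SE shares 70/30%. At R² = 5%, 10% and 20% the unstratified test had size of about 4.4%, 4.0% and 2.7%, and power of 77%, 76% and 72%. The van Elteren test had power of about 78% to 79%. This matches the formula, with losses of about 1 to 3 points at 5% to 10% and 6 to 7 points at 20%.

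**Simulation 2.** 3,000 runs, 280 per arm, different assumed stratum sizes. Scores were rounded to eighths on a 1-to-5 scale, like the mean of eight items, and the shift was 0.24 total SD, so power levels are not comparable with those above.

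| R² | Size, unstratified | Size, van Elteren | Power, unstratified | Power, van Elteren |
|---|---|---|---|---|
| 0 | 4.9% | 4.7% | 78% | 77% |
| 10% | 4.3% | 5.6% | 80% | 83% |
| 30% | 2.3% | 4.9% | 82% | 90% |

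The Monte Carlo standard error of a 5% size is √(0.05 × 0.95/3000) = 0.4 points, so 5.6% is within noise of 5%. The direction agrees: no difference when the strata explain nothing, and a growing loss as they explain more.

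**Attrition.** Size does not depend on n. SAP 4.1 uses a 7% annual dropout or discontinuation rate in its own simulations. Applied for three years, this leaves 280 × 0.93³ = 225 per arm. The same power formula then gives losses of about 1.8, 3.8 and 8.5 points, so the order of magnitude stands.

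**The case against.** **The test is valid and only informational.** This stands. Omitting the strata cannot produce a false claim. QOL is exploratory in protocol Section 3 and lies outside the gatekeeping sequence of SAP 8.2. Stratified tests for confirmatory endpoints do not oblige the SAP to stratify an informational p-value. Item summaries, frequency tables, estimates and intervals will be reported whatever the p-value shows. This limits the weight of the point but does not remove the inefficiency.

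**The size of the loss is assumed.** This also stands. The variance shares, stratum shares and shift come from no document, and at R² = 0 the loss is nil.

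**A stratified p-value would not match the interval.** The Hodges-Lehmann estimate and Moses interval belong to the unstratified two-sample test. The mismatch is real, and any fix must state it.

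**A stronger reading to avoid.** A reader might infer that the tests also run at Month 48, when no child randomized to Vehicle is assigned to Vehicle, because SAP 8.4 mentions several timepoints and sets no last visit. The documents do not support this. SAP 8.3 says "Data collected after Month 36 will be considered exploratory analysis and summarized separately using descriptive statistics only", grouped by treatment pathway, and protocol 9.4.9 likewise makes data after Month 36 exploratory and descriptive. SAP Section 4 splits groups by initial and current treatment after re-randomization. As far as the extracted schedule can be read, QOL is collected at several visits through Month 36, so the mention of multiple timepoints does not imply a Month 48 test. SAP 8.4 lacks only a cross-reference to these rules; the sections do not contradict each other.

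**Conclusion.** The point holds as a minor one. The QOL rank test is valid but does not use the stratified design. Its nominal 5% level is really about 4.4%, 3.9% or 2.8% if age and SE explain 5%, 10% or 20% of score variance. At 280 per arm and a 0.24 SD shift, the matching power loss is about 1 to 3 points at 5% to 10% and about 6 to 7 points at 20%. These figures rest on assumed variance shares, an assumed shift and balanced allocation within strata. If the strata do not predict QOL, nothing is lost. No conclusion in either regulatory hierarchy depends on it. The missing visit limit and grouping in SAP 8.4 need a clarifying sentence and are not an error in the planned analysis.

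**What to change.** In SAP 8.4, take the dose-versus-Vehicle p-value from the van Elteren (stratified Wilcoxon) test with the randomization strata. Prespecify how sparse strata are pooled, for example by merging neighbouring age classes when a cell falls below a stated count. Keep the Hodges-Lehmann estimate and Moses interval, labelled as unstratified support, or replace them with stratified analogues.

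As a clarification, add one sentence: these tests compare initial randomized arms at visits through Month 36, and Month 48 QOL is descriptive by Part 2 pathway, as SAP 8.3 and protocol 9.4.9 already provide.

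The cost is a few sentences of SAP text, a pooling rule and a small programming change, with no new data. There are two small downsides. The p-value and the unstratified interval are no longer exact counterparts and could disagree near the 5% boundary. The van Elteren test is also usually referred to a large-sample distribution, so the exact p-value is given up unless a within-stratum permutation version is programmed.
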